Screening Visits: Participants will be recruited from the community via flyers, newspaper postings, and other media outlets. Screening visits will take place on the Behavioral Pharmacology Research Unit at the Johns Hopkins Bayview Medical Center. Individuals will complete a phone-screen to assess for initial eligibility and will be invited for a clinic-based visit to confirm final eligibility. During this visit, participants will first review an informed consent form with a staff member and discuss the study before

providing voluntary informed consent to participate. Participants will then complete a series of measures to establish study eligibility, including a demographics questionnaire, self-reported opioid use and withdrawal, a past 30-day timeline follow back for drug and alcohol use, assessments of DSM-5 drug and alcohol use disorders, the Stop-Bang questionnaire assessment of sleep apnea, psychiatric functioning (MINI International Neuropsychiatric Interview [Sheehan et al., 1998]), and the Columbia Suicide Severity Rating Scale (Posner et al., 2011). Participants will provide a blood sample that will be tested for complete blood count and comprehensive metabolic panel, provide a urine sample that will be tested for evidence of opioid and other drug use, and pregnancy (when applicable). Either during the Screening or admission day, participants will complete a medical history and physical examination with qualified medical staff to determine final study eligibility. The physical examination will include an electrocardiogram (ECG) to determine if the participant has any heart abnormalities, and the Brief Pain Inventory to quantify current chronic pain issues (Cleeland et al., 1994). Opioid withdrawal scales will be collected at the end of the Screening visit to help confirm opioid physical dependence.

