Buprenorphine Induction and Stabilization: Participants will be inducted onto buprenorphine prior to beginning the buprenorphine taper. Induction may occur up to 3 weeks prior to admission to the CRU. Participants will be required to show evidence of opioid withdrawal (as per ratings on the COWS) and will receive incremental doses of buprenorphine throughout the day, up to a maximum of 16mg of buprenorphine on the induction day. The induction protocol will be conducted as clinically indicated, based upon medical team recommendations. To increase comfort during the induction, the medical team may administer the PRN concomitant medications that are approved for the taper protocol as well as clonidine. Participants may then be maintained on buprenorphine as an outpatient for up to 3 weeks before CRU admission. Briefly maintaining participants on buprenorphine will enable the study to retain participants between Screening and CRU admission, as the CRU has restricted access for protocols requiring weekend coverage. Participants who are maintained on buprenorphine as an outpatient will receive blister packages of sublingual buprenorphine for outpatient administration and may receive up to 24mg/day (beginning the day after induction) during this period. During the stabilization period between Screening and Admission, participants will be required to visit the clinic on a weekly basis to exchange blister packages. Participants may receive assistance (e.g., bus tokens) from the study to help facilitate transportation to the BPRU on those days. Any participant receiving >16 mg as an outpatient will be transitioned to 16mg on the CRU admission day. Participants who are inducted onto buprenorphine on the CRU admission day will follow an identical induction procedure and will only receive up to 16mg.

Clinical Research Unit (CRU): Following confirmation of eligibility, participants will be admitted onto a residential CRU that is located on the Bayview Medical Campus. Participants will reside on the CRU for up to 11 days (10 nights) and will be allowed to smoke cigarettes ad libitum in a designated smoking area during their stay. Female participants will provide a sample of blood upon admission that will be analyzed for levels of progesterone and estrogen.

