- Have no clinically significant chronic medical or surgical disorders or conditions that are judged by the investigators to prevent participation.

Exclusion Criteria:

- Seeking or currently enrolled in methadone or buprenorphine maintenance treatment for OUD
- Pregnant or breast feeding.
- Have evidence of physical dependence on alcohol or benzodiazepines that requires medical detoxification.
- Have a known allergy to the study medications.
- Past 30-day prescribed use of suvorexant or benzodiazepines for the indication of insomnia.
- Current use of an SSRI or MAO inhibitor for depression or insomnia, or other medications that are contraindicated with suvorexant.
- Current narcolepsy, restless leg syndrome, or sleep paralysis.
- High risk for current sleep apnea as assessed via the Stop Bang questionnaire.
- Current major depressive disorder.
- Past year suicidal behavior as assessed via the Columbia Suicide Severity Rating Scale
- Severe hepatic or renal impairment, defined as:
 - AST or ALT $>3x$ ULN.
 - Total Bilirubin $>2x$ ULN.
 - Creatinine $>1.5x$ ULN.
- Have circumstances that would interfere with study participation (e.g., impending jail).

6. Drugs/ Substances/ Devices

- a. The rationale for choosing the drug and dose or for choosing the device to be used.

Suvorexant (SUVO): SUVO is FDA-approved for the treatment of insomnia and is an ideal candidate for evaluation because it is intended for PRN administration, improves sleep architecture after a single dose (Herring et al., 2016b; Sun et al., 2013), and does not cause a withdrawal syndrome after abrupt discontinuation even when it has been administered chronically for several weeks (Herring et al., 2016b). This study utilizes two doses of SUVO (20 and 40mg) to evaluate which dose has a superior risk/benefit profile, although we do not anticipate a high rate of adverse events for either dose. The most effective dose can then be used in future clinical trials as well as in practice for the treatment of sleep disturbance during opioid withdrawal. Participants will be given their medication dose in two weight and color-matched capsules, containing either two 20mg SUVO (40mg dose), two 10mg SUVO (20mg dose), or two placebo capsules. As an added precaution, participants will be allowed to reduce their dose from two to one capsule (representing a 50% dose decrease) if they experience negative side-effects and would prefer a lower dose.

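### The medical history, physical examination and ECG may be done up to 21 days after the first buprenorphine dose; tie them to that dose instead.

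*Combined protocol and SAP*

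**What the plan says.** Section 4.a, Screening Visits, states when the history and examination take place: "Either during the Screening or admission day, participants will complete a medical history and physical examination". Their stated purpose is to settle final eligibility. The ECG has the same timing: "The physical examination will include an electrocardiogram (ECG) to determine if the participant has any heart abnormalities".

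Section 4.a, Buprenorphine Induction and Stabilization, describes two routes. Some participants are inducted on the day they enter the CRU. Others start earlier: "Induction may occur up to 3 weeks prior to admission to the CRU". The second group takes blister packs home and "may receive up to 24mg/day (beginning the day after induction) during this period". Between induction and admission, "participants will be required to visit the clinic on a weekly basis to exchange blister packages". On induction day, "the medical team may administer the PRN concomitant medications that are approved for the taper protocol as well as clonidine".

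Section 5 includes a general medical criterion, "Have no clinically significant chronic medical or surgical disorders or conditions that are judged by the investigators to prevent participation", and an exclusion, "Have a known allergy to the study medications". Section 8.a, item 2, advises against buprenorphine/naloxone in patients with respiratory distress, known allergy, or a cardiac history such as long QT syndrome or severe hypotension.

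**The concern.** The choice between Screening and admission day suits someone inducted on the CRU, because both days can come before the first dose. It does not suit someone inducted as an outpatient, for whom admission day may fall three weeks after dosing began. The text does not separate the two cases.

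The order matters because history, examination and ECG are the main means of finding the conditions named in sections 5 and 8.a. Done on admission day, they cannot inform the decision to start buprenorphine or to give clonidine. An ECG abnormality first seen then could not be dated to before or after dosing. A participant found ineligible at that point could already have had up to three weeks of study-supplied buprenorphine, mostly taken at home.

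The issue is participant safety and the sequencing of eligibility checks. It does not bear on the randomized comparison.

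**Working it through.** **Inputs**

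- Latest permitted day for history, examination and ECG: CRU admission day, called day 0 (section 4.a, Screening Visits).
- Earliest permitted induction: 3 weeks before admission (section 4.a, Buprenorphine Induction and Stabilization). Section 6.a gives the same three-week maximum.
- Maximum dose on induction day: 16 mg. Maximum outpatient dose from the following day: 24 mg/day (same subsection of 4.a).
- Planned enrolment: 45 (section 7.c).

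**Maximum lag**

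- 3 weeks × 7 = 21 days, so the earliest induction is day −21.
- Lag = day 0 − day (−21) = 21 days.
- If the checks must precede the first dose, the maximum lag after dosing is 0 days.

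**Maximum buprenorphine before the checks**

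- Induction on day −21: 16 mg.
- Outpatient dosing on days −20 to −1: 20 days × 24 mg = 480 mg.
- Total: 16 + 480 = 496 mg over 21 days.
- Weekly pack exchanges fall about 7 and 14 days after induction, so about two visits come before admission.

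**Does any other text close the gap?**

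| Provision | Where | Requires history, examination or ECG before the first dose? |
|---|---|---|
| Withdrawal rated on the COWS; medical team directs induction | 4.a, Induction | No; neither assessment nor ECG is specified |
| Eligibility confirmed before CRU admission | 4.a, Clinical Research Unit | No; it precedes admission, not induction |
| Weekly clinic visits | 4.a, Induction | No; the stated purpose is pack exchange |
| Blood count, metabolic panel, urine drug and pregnancy tests, Stop-Bang, MINI, suicide scale | 4.a, Screening Visits | No; done at Screening, but none is an ECG, general medical history or physical examination |
| Clonidine withheld below 80/60 | 8.a, item 5 | No; a blood-pressure check only |

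**Number affected.** The documents do not say how many participants will be inducted as outpatients or when they will be examined. The range is 0 (everyone examined at Screening or inducted on the CRU) to all 45, plus anyone inducted but never admitted.

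**What is not affected.** Blinded medication starts on the evening before Taper Day 1, after admission, so suvorexant always follows the examination. Anyone who fails the examination on admission day would leave before randomization. Sample size, power and alpha do not change.

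**The case against.** The strongest reply is that this is a permissive reading of a loosely drafted sentence. The checks sit under the Screening heading, and the admission-day option may have been written only for those inducted on the CRU. Nothing says that anyone intends to induct early and examine late. The medical team directs induction, and silence about the history they take is weak evidence that they take none. The list of screening measures is introduced as illustrative, and a phone screen comes first; a known allergy or cardiac history can be self-reported at either. Section 5 has no QTc or other ECG threshold, so an earlier ECG would inform judgement without enforcing a stated limit. Clonidine is expected in very few patients and has its own blood-pressure limit. Buprenorphine is used on-label, and discharged patients receive naloxone and referral. The 496 mg figure stacks every maximum, and cumulative dose does not measure the risks at issue, since an allergy or cardiac contraindication matters from the first dose.

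Most of this stands as mitigation. It makes harm less likely and makes the dose total a description of how wide the permission is, not a measure of risk. It does not show that the protocol requires the checks before dosing, and no section does. Clinical judgement lowers the risk but does not replace a written requirement before the first dose. If staff already examine everyone first, the change only records that practice.

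**Conclusion.** The concern holds. For outpatient inductees, the protocol as written permits the history, examination and ECG to follow the first buprenorphine dose, and any induction clonidine, by up to 21 days and up to 496 mg of buprenorphine. This is a permission left too wide. It is not a contradiction between sections, and it is not evidence of what staff do.

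Confidence is high on what the text allows. How often it would happen cannot be determined from the documents. The 496 mg total assumes the longest interval and the highest permitted dose on every day. The point should be fixed because it concerns participant safety and the remedy is cheap. It has no bearing on the statistical validity of the trial.

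**What to change.** In section 4.a, Screening Visits, replace the timing sentence with:

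> The medical history, physical examination and ECG will be completed and reviewed by qualified medical staff before the first study dose of buprenorphine or clonidine. For participants inducted on the CRU, these may be done on admission day, before induction.

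For outpatient inductees, add a short interval-history update at admission, with a repeat ECG at the medical team's discretion.

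No new type of test is needed, since all three assessments are already planned. The costs are small:

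- Some examinations and ECGs will be done on people who are never admitted.
- Results for outpatient inductees may be up to about three weeks old at admission. The plan already accepts this for anyone examined at Screening, and the interval history limits it.
- Induction may occasionally be delayed if the examination or ECG cannot be done at Screening. Outpatient buprenorphine exists partly to retain people waiting for a CRU place, so scheduling these checks at the Screening visit should be the default.

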Brief Sleep Hygiene Education: During stabilization, staff will conduct a brief educational session with participants to provide information regarding appropriate sleep hygiene (Doshi et al., 2017). This session will ensure all participants have the same understanding of healthy sleep behaviors before the taper begins, to minimize the impact that differences in sleep hygiene has, and better isolate the impact of SUVO on study outcomes.

Overdose Education: During the stabilization period, participants will also complete a brief opioid overdose prevention computerized education session (developed by Co-I Dunn under NIDA R21DA035327).

Randomization to Group: Participants will be stratified into experimental group based on (a) baseline Pittsburgh Sleep Quality Index (PSQI) (<5/≥5), (b) peak SOWS ratings during buprenorphine induction (≤10/>10), (c) buprenorphine stabilization dose (<16mg/16mg), and (d) sex (M/F). Randomization will occur via a minimization procedure to balance the distribution of these characteristics

across the experimental groups. Study pharmacist staff, who have no direct participant contact, will oversee randomization and dispensing of study medications.

Taper Phase (4 days): Participants will undergo an open-label, step-wise buprenorphine taper. An open-label phase is necessary because buprenorphine placebo tablets/filmstrips are not available; however, this open-label design feature is of value because it increases the overall generalizability of the study results.

Post-taper Phase (4 days): Participants will continue study participation for four days (three nights) following buprenorphine discontinuation, to capture the full course of opioid withdrawal.

Study Medications: Double-blind study medication dosing will begin on the evening before Taper Day 1. Study medications will either be 20mg SUVO, 40MG SUVO, or placebo, which will be administered prior to bedtime. Though participants will be reminded to practice good sleep hygiene, no contingencies or consequences will be associated with their sleep behavior. This is because our extensive experience suggests that participants who are unable to sleep at night will attempt to sleep during the day; all sleep attempts will be captured by wrist actigraphy and nightly questionnaires and evaluated as outcome data. Placing contingencies on sleep parameters (such as no day-time sleeping) could also prompt attrition.

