The first primary outcome for this study will be total sleep time during opioid withdrawal as determined by EEG, and supplemented by actigraphy and self-report.

The second primary outcome for this study is abuse liability, which will be assessed via next day measures of Drug Liking measured on a 0-100 point VAS.

b. Secondary outcome variables.

(1) Secondary outcomes from the Sleep Profiler EEG will include measures of sleep continuity and architecture

(2) Secondary actigraphy outcomes will include sleep and activity-related outcomes

(3) Secondary self-report sleep ratings will include self-reported sleep measures

(4) Opioid withdrawal severity, assessed via the subjective opiate withdrawal scale.

(5) Other secondary outcomes include a hypothetical purchasing task, other self-report VAS measures of abuse liability (e.g. drug effect, good effect, bad effect, perceived drug value), self-reported measures of drug craving, VAS opioid withdrawal, stress; diurnal cortisol; vital signs; and retention in treatment.

c. Statistical plan including sample size justification and interim data analysis.

Power Analyses: In order to support the planned 2 and 3 group analyses (comparing 20mg SUVO, 40mg SUVO, and placebo), we used G-power to derive sample sizes from previously reported effect sizes in clinical trials on SUVO and hypothetical opioid purchase task data; both displayed large effect sizes (≥ 0.70). A total sample size of 36 participants (12 per group) would provide 95% power to detect an effect size of 0.70 for difference in total sleep time (Primary Aim 1) and difference in the opioid demand curve (Secondary Aim 1). A study on the abuse liability of SUVO, zolpidem, and placebo in non-ODU patients (Schoedel et al., 2016) reported a medium to large effect size on drug liking (0.45), suggesting a total sample size of 34 would provide 90% power to detect an effect size of 0.45 for Primary Aim 2. To protect against participant drop out, we are proposing to enroll 15 participants per medication group (total N=45).

Analyses: All Primary Outcomes (total sleep time, opioid withdrawal severity, and abuse liability) will be compared as a function of group (20mg SUVO, 40mg SUVO, and placebo; or SUVO [collapsed] vs placebo) and phase (taper vs. post-taper), as well as group by day (7 nights) using 2-factor Proc Mixed analyses with Tukey posthoc testing. Both peak values and Area-under-the-curve (AUC) values of total sleep time, SOWS scores, and Drug Liking

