will be derived for (a) the entire study, (b) the taper period, and (c) the post-taper period. These outcomes will be compared as a function of group and group x phase using independent groups t-tests and ANOVAs with Tukey post-hoc for pairwise comparisons. If data does not meet ANOVA assumptions, mixed model regressions will be used.

Secondary outcomes from the Sleep Profiler EEG may include measures of sleep continuity (sleep latency, sleep efficiency [total sleep time/time spent in bed], wake after onset [WASO], number of awakenings) and architecture (time spent in stage 1, stage 2, stage 3, and rapid eye movement [REM] sleep). (b) Secondary actigraphy outcomes may include wake after sleep onset (WASO), time spent napping, number of naps, and total activity. (c) Secondary self-report ratings may include subjective WASO, VAS sleepiness and quality of sleep, and Stanford Sleepiness Scale score. **Analyses:** All outcomes will be compared as a function of group (20mgSUVO, 40mg SUVO, and placebo) and phase (taper vs. post-taper), as well as group by day (7 nights) using 2-factor Proc Mixed analyses with Tukey posthoc testing. Area-under-the-curve (AUC) values for the entire study and the taper and post-taper periods will then be derived and compared as a function of group and group x phase using independent groups t-tests and ANOVAs with Tukey post-hoc for pairwise comparisons. If data does not meet ANOVA assumptions, mixed model regressions will be used.

Secondary actigraphy outcomes may include wake after sleep onset (WASO), time spent napping, number of naps, and total activity. Secondary self-report ratings may include subjective WASO, visual analogue scale (VAS) sleepiness and quality of sleep, and Stanford Sleepiness Scale score. All outcomes will be compared as a function of group (20mg SUVO, 40mg SUVO, and placebo) and phase (taper vs. post-taper), as well as group by day (7 nights) using area-under-the-curve (AUC). The taper and post-taper periods will then be derived and compared as a function of group and group x phase using independent groups t-tests and ANOVAs with Tukey post-hoc for pairwise comparisons. If data does not meet ANOVA assumptions, mixed model regressions will be used.

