Secondary measures will be additional ratings on the hypothetical purchase task, SOWS and VAS ratings of opioid withdrawal, VAS ratings of abuse liability, self-reported craving, self-reported stress, perceived drug value, and diurnal salivary cortisol (measured via AUC values and mean daily cortisol) and cortisol/ACTH ratios. Purchase task data will be fit to opioid demand curves for comparison. **Analyses:** All outcomes will be compared as a function of group (20mg SUVO, 40mg SUVO, and placebo) and phase (taper vs. post-taper), as well as group by day (7 nights) using area-under-the-curve (AUC). The taper and post-taper periods will then be derived and compared as a function of group and group x phase using independent groups t-tests and ANOVAs with Tukey post-hoc for pairwise comparisons. If data does not meet ANOVA assumptions, mixed model regressions will be used. Exploratory analyses will include linear and multivariate regression models to examine the relationship between measures of sleep, stress, opioid withdrawal, and craving. Logistic regression will be used to examine the relationship between sleep, stress, opioid withdrawal, and craving on the likelihood of treatment attrition.

d. Early stopping rules.

Patients will discontinue their study participation if they request to be discharged, have a serious adverse event, or if the study physicians decide it is in the patient's best interest to be removed from the study. All patients will be discharged with naloxone, opioid overdose education, and referral to outpatient OUD treatment.

8. Risks

a. Medical risks, listing all procedures, their major and minor risks and expected frequency.

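### Allocation is minimised on four factors that no planned group comparison includes, so between-patient tests are conservative to the extent that those factors predict the outcome

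*Combined protocol and SAP*

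**What the plan says.** Section 4.a, Randomization to Group, names four two-level factors: PSQI (below 5, or 5 and above), peak SOWS during induction (up to 10, or above), stabilization dose (below 16mg, or 16mg) and sex. It then says: "Randomization will occur via a minimization procedure to balance the distribution of these characteristics". The algorithm, the factor weights and any random element are not described.

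Section 7.c compares the primary outcomes by group "and phase (taper vs. post-taper), as well as group by day (7 nights) using 2-factor Proc Mixed analyses with Tukey posthoc testing". For the peak and AUC values it adds: "These outcomes will be compared as a function of group and group x phase using independent groups t-tests and ANOVAs with Tukey post-hoc". The paragraphs on secondary outcomes use the same terms. The terms named are group (three arms, or SUVO collapsed against placebo), phase and day. No minimisation factor or other baseline covariate is named. The only regressions with further variables relate outcomes to one another: "Exploratory analyses will include linear and multivariate regression models to examine the relationship between measures of sleep, stress, opioid withdrawal, and craving". They are not adjusted group comparisons.

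**The concern.** An unadjusted comparison of arms estimates its standard error as if a factor's distribution could differ freely between arms. Minimisation prevents most of that. The variance due to the factor stays in the residual, although it no longer contributes much to the difference between arms. The reported standard error is then larger than the true one, and the test rejects a true null less often than its nominal rate.

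At stake is precision, not bias or false positives. With 12 to 15 participants per arm, the trial may give up information that its allocation has already secured. Section 1 says that the dose found most efficacious here goes into a subsequent study, so an avoidable loss of power for the group comparisons carries forward.

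**Working it through.** **1. The plan's own figure.** Section 7.c states 95% power with 36 participants (12 per group) at an effect size of 0.70. Neither the metric nor alpha is stated; alpha = 0.05 is assumed. For a one-way ANOVA on three groups without covariates, read as Cohen's f, λ = f² × N = 0.49 × 36 = 17.64 with 2 and 33 degrees of freedom. Power is 95.7%, so the figure reproduces. Read as a standardised mean difference between two arms of 12, 0.70 gives 37.5% (two-sided t-test). The stated power is therefore that of an unadjusted ANOVA with f = 0.70. In three arms this corresponds to an extreme-arm difference of 0.70 × 3/√2 = 1.48 SD (two arms at one end) to 0.70 × √6 = 1.71 SD (one arm midway).

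**2. The mechanism by formula.** Take one value per patient, total SD 1, 15 per arm, and factors that explain a share R² and are perfectly balanced.

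- SE reported without the factors: √(2/15) = 0.365.
- True SE: √((1 − R²) × 2/15), which is 0.346, 0.327 and 0.306 at R² = 0.1, 0.2 and 0.3.
- Ratio: 1/√(1 − R²) = 1.05, 1.12 and 1.20.
- The pairwise critical value on 42 degrees of freedom is 2.018. It acts as 2.018 × ratio = 2.13, 2.26 and 2.41. The nominal 5% test then has a size of about 3.9%, 2.9% and 2.0%.

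**3. Simulation of the minimisation.** Assumptions: three arms, N = 45, four equally weighted binary factors with assumed prevalences 0.60, 0.50, 0.50 and 0.35, one summary value per patient, 4,000 null runs per setting. The last two columns give the type I error of the nominal 5% F-test.

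| R² | Reported SE | True SE | Ratio | Factors omitted | Factors included |
|---|---|---|---|---|---|
| 0 | 0.365 | 0.368 | 0.99 | 5.1% | 5.1% |
| 0.1 | 0.365 | 0.348 | 1.05 | 3.7% | 4.7% |
| 0.2 | 0.367 | 0.326 | 1.13 | 2.4% | 4.8% |
| 0.3 | 0.368 | 0.311 | 1.18 | 1.7% | 5.1% |
| 0.4 | 0.368 | 0.299 | 1.23 | 1.1% | 5.7% |

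The simulation error on type I error is about 0.3 points. A random element of 0.8 in the minimisation gave the same pattern (2.0% at R² = 0.3).

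For the pairwise test, separate simulations gave a size of 2.9–3.7% at R² = 0.2 and 2.1–2.7% at R² = 0.3. Power for a 1 SD pairwise difference at N = 45 was 78% without the factors against 84% with them at R² = 0.2, and 79% against 89% at R² = 0.3. At R² = 0.1 it was 76% against 79%.

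**4. Power at the planned 36 evaluable participants** (F-test, 2,000 runs, simulation error about 1 point).

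| R² | f = 0.35, omitted | f = 0.35, included | f = 0.70, omitted | f = 0.70, included |
|---|---|---|---|---|
| 0 | 41% | 40% | 96% | 95% |
| 0.1 | 41% | 45% | 96% | 97% |
| 0.2 | 39% | 50% | 97% | 98% |
| 0.3 | 37% | 56% | 97% | 99% |
| 0.4 | 34% | 61% | 98% | 99.8% |

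**5. Which contrasts are affected.** A factor that is fixed within a patient and has a constant effect adds the same amount on every night. It cancels from differences between nights or phases, so the group-by-day and group-by-phase contrasts are not affected. It remains in the group main effect and in the AUC and peak comparisons.

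**The case against.** The strongest reply is that this is a refinement whose size nobody can state. The documents call none of the four factors prognostic and give no R² for sleep time, still less for Drug Liking of a blinded drug. If R² is nil, adjustment loses slightly. At the plan's own f = 0.70 power is already high. The error is also in the safe direction: no bias and no excess of false positives. All of this stands, and it limits the size of the point. It does not remove it. The investigators chose these factors as worth balancing, SOWS is itself an analysed outcome, and the loss from adjusting for irrelevant factors is about one point of power.

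A reader might also infer that leaving out induction route makes the error bars too wide. Section 4.a says "Induction may occur up to 3 weeks prior to admission to the CRU", while others are inducted on the admission day, and route is neither a minimisation factor nor a model term. The inference fails because route is not balanced by the allocation. The ordinary standard error already allows for chance imbalance in it. In simulation, with route explaining 10, 20 or 30% of variance, reported and true SE were 0.364 and 0.361, 0.365 and 0.371, 0.366 and 0.362, with type I error 5.0, 4.9 and 5.4%. Nor do the documents present route as the largest difference before randomisation. They bring the routes partly together: "Any participant receiving >16 mg as an outpatient will be transitioned to 16mg on the CRU admission day", and everyone then has a 3-day stabilization period (section 6.a).

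**Conclusion.** The point holds in a limited form. Four factors are used to allocate and none is used to analyse. For the group main effect, AUC and peak comparisons, this makes the reported standard errors too large and the tests conservative in proportion to how well the factors predict the outcome: nothing at R² = 0, about 5% excess SE at 0.1, 13% at 0.2 and 18% at 0.3. The power at stake is at most about 2 points at f = 0.70. It is larger if the true effect is smaller, for example 39% against 50% at f = 0.35 and R² = 0.2.

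These sizes rest on an assumed R², assumed prevalences, equal weights and one value per patient. The documents do not support the stronger statements that the factors are known to be prognostic, that every planned test is affected, or that the omission of induction route invalidates anything.

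**What to change.** In section 7.c, name the four minimisation factors, as coded for allocation, as fixed covariates in the group models for the primary outcomes. For AUC and peak values, use ANCOVA with these factors in place of the t-test and ANOVA. State this before unblinding, so that there is no later choice between adjusted and unadjusted results.

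The cost is a wording change, four model degrees of freedom (from 42 to 38 with 45 participants in three arms) and about one point of power if the factors turn out not to be prognostic. No new data are needed. Days on buprenorphine before Taper Day 1, or induction route, may be added as an optional precision covariate; the validity of the tests does not depend on it, and the minimisation scheme need not change.
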